**Table 1 Objectives and Corresponding Endpoints (cont.)**

Secondary Efficacy Objective (cont.)	Corresponding Endpoints
To evaluate the efficacy of atezolizumab/enzalutamide compared with enzalutamide alone (cont.)	
 
• rPFS probability at 6 and 12 months
 
• PSA response rate, defined as a > 50% decrease in PSA from baseline that is confirmed after ≥ 3 weeks by a consecutive confirmatory PSA measurement
 
• Time to PSA progression, defined as the time from randomization to the time of PSA progression, as defined per the PCWG3 criteria (Scher et al. 2016): 
 
In patients with no PSA decline from baseline, PSA progression is defined as a ≥ 25% increase and an absolute increase of ≥ 2 ng/mL above the baseline value, ≥ 12 weeks after baseline.
 
In patients with an initial PSA decline from baseline, PSA progression is defined as a ≥ 25% increase and an absolute increase of ≥ 2 ng/mL above the nadir value, which is confirmed by a consecutive second value obtained ≥ 3 weeks later.
 
 
 
• Objective response rate in soft tissue lesions, defined as the proportion of patients with either a CR or PR on two consecutive occasions ≥ 6 weeks apart, as determined by the investigator through use of PCWG3 criteria (see Appendix 2)
 

Exploratory Efficacy Objective	Corresponding Endpoints
• To evaluate the efficacy of atezolizumab/enzalutamide compared with enzalutamide alone	
 
• DOR in soft tissue lesions, defined for patients who had an objective response in soft tissue as the time from the first documented objective response in soft tissue to radiographic disease progression, as determined by the investigator through use of PCWG3 criteria
 
• DCR, defined as the proportion of patients with a best response of confirmed CR or PR or stable disease in soft tissue lesions per PCWG3-modified RECIST v1.1 and/or no confirmed radiographic disease progression on bone scan per PCWG3 criteria (see Appendix 2)
 
• Modified progression free survival based on radiographic disease progression and unequivocal clinical progression, defined as the time from randomization to the earliest occurrence of one of the following: 
 
Radiographic disease progression per PCWG3 criteria (as defined above)
 
Unequivocal clinical progression characterized as at least one of the following: 
 
Symptomatic skeletal-related event (as defined above)
 
Deterioration in ECOG performance status by at least two points that is attributed to disease progression
 
Initiation of next systemic anti-cancer therapy
 
 
 
 
 

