
 
•To evaluate the efficacy of atezolizumab/enzalutamide compared with enzalutamide alone
 
	
 
•OS probability at 12 and 24 months
 
•Time to first SSE An SSE is defined as external beam radiation therapy to relieve skeletal symptoms (including initiation of radium-223 dichloride or other types of radionuclide therapy to treat symptoms of bone metastases), new symptomatic pathologic bone fracture, clinically apparent occurrence of spinal cord compression, or tumor related orthopedic surgical intervention.
 
•rPFS, as assessed by the investigator, and adapted from the PCWG3 criteria (Scher et al. 2016; see Appendix 2). rPFS is defined as the time from randomization to the earliest occurrence of one of the following: A patient is considered to have progressed by bone scan if: The first bone scan with <math>\geq 2</math> new lesions compared to baseline is observed <math>< 12</math> weeks from randomization and is confirmed by a second bone scan taken <math>\geq 6</math> weeks later showing <math>\geq 2</math> additional new lesions (a total of <math>\geq 4</math> new lesions compared to baseline); the date of progression is the date of the first post-treatment scan, OR After the first post-treatment scan, <math>\geq 2</math> new lesions are observed relative to the first post-treatment scan, which is confirmed on a subsequent scan <math>\geq 6</math> weeks later; the date of progression is the date of the post-treatment scan when <math>\geq 2</math> new lesions were first documented.
 
Progression of soft tissue lesions, as defined per PCWG3 modified RECIST v1.1
 
Death from any cause
 

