### **3.4.7 Rationale for the Use of Response Criteria**

#### **3.4.7.1 PCWG3 Criteria**

Measurable disease occurs infrequently in prostate cancer, whereas bone metastases develop in upwards to 90% of patients (Pezaro et al. 2013). An international expert committee of prostate cancer investigators, the PCWG3, met between 2012 and 2015 to formulate criteria to define meaningful clinical endpoints in mCRPC (Scher et al. 2016). This study will follow the expert recommendations to assess radiographic disease progression (see [Appendix 2](#)).

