#### **6.4.2.3 Objective Response Rate in Soft Tissue Lesions**

The analysis population for objective response rate (ORR) will be all patients in the ITT population with measurable soft tissue lesions at baseline.

ORR is defined as the proportion of patients who had a confirmed response in soft tissue lesions. An estimate of ORR will be calculated for each treatment arm, and its 95% CI will be calculated using the Clopper Pearson method. The CI for the difference in ORRs between the two treatment arms will be determined using the normal approximation to the binomial distribution.

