#### **6.4.3 Exploratory Efficacy Endpoints**

The methodologies outlined for the ORR in soft tissue lesions analysis will be used for the DCR analysis.

The following exploratory time-to-event endpoints will be analyzed using the same methods as outlined in the section on secondary time-to-event endpoints.

- Modified PFS based on radiographic disease progression and unequivocal clinical progression
- DOR in soft tissue lesions
- Time to initiation of next systemic anti-cancer therapy
- Time to unequivocal clinical progression

DOR will be assessed in patients who had an objective response in soft tissue lesions as determined by the investigator.

DOR is defined as the time from the first occurrence of a CR or PR (whichever status is recorded first) until the first date progressive disease or death is documented, whichever occurs first. Patients who have not progressed and who have not died at the time of

analysis will be censored at the time of last tumor assessment date. If no tumor assessments were performed after the date of the first occurrence of a CR or PR, DOR will be censored at the date of the first occurrence of a CR or PR plus 1 day.

The statistical methods applied to DOR will be the same as for rPFS described above. However, it should be noted that DOR is evaluated in a non-randomized subset of patients (those who achieved an objective response in soft tissue); therefore, results of this analysis will be provided for descriptive purposes only.

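### The disease control rate (DCR) joins its soft tissue and bone criteria with *and/or*, so progression in one compartment can still count as disease control

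*Combined protocol and SAP*

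**What the plan says.** Table 1 in Section 2 lists DCR under the "Exploratory Efficacy Objective". It counts patients whose best soft tissue outcome is a confirmed response or stability, "and/or no confirmed radiographic disease progression on bone scan per PCWG3 criteria". The synopsis uses the same connective, so this is not a slip in one place. Neither text says that both criteria must hold when both compartments are diseased, or that a criterion applies only to a compartment involved at baseline.

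Section 6.4.3 adds one sentence on analysis: "The methodologies outlined for the ORR in soft tissue lesions analysis will be used for the DCR analysis". The ORR analysis in Section 6.4.2.3 uses Clopper-Pearson intervals for each arm and a normal approximation for the difference. Its population is defined this way: "The analysis population for objective response rate (ORR) will be all patients in the ITT population with measurable soft tissue lesions at baseline".

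Radiographic progression-free survival (rPFS) in the same Table 1 follows the opposite logic: "rPFS is defined as the time from randomization to the earliest occurrence of one of the following", the list being bone progression, soft tissue progression and death. Under Appendix 2, soft tissue progression needs no confirmatory scan, whereas bone progression needs a second scan at least 6 weeks later.

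**The concern.** *And/or* is the inclusive or, so an analyst who programs the definition as written will accept either criterion. Two kinds of patient then enter the numerator although their disease is not controlled: those with soft tissue progression as best outcome and no confirmed bone progression, and those with stable soft tissue disease and confirmed bone progression.

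The bone criterion is also easy to meet, because it asks only that no confirmed progression be recorded. Read literally, a patient with no bone disease, or one who dies or leaves before the confirmatory scan, satisfies it even with soft tissue progression.

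At stake is the meaning of a published proportion. Two analysts could report very different DCRs from the same data, one by coding the text and one by coding what was probably intended.

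**Working it through.** The documents state no DCR, component rate, correlation or power for this endpoint, so there is no figure to reproduce. The check is on the logic, followed by an illustration on assumed rates.

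**Logic.** Let A = soft tissue criterion met and B = bone criterion met.

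- As written: P(A or B) = P(A) + P(B) − P(A and B).
- Both required: P(A and B).
- Excess: P(A) + P(B) − 2·P(A and B), which is the proportion of patients meeting exactly one criterion. It cannot be negative, and it is positive once a single patient is discordant.

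**Illustration (assumed values, patients with disease in both compartments).** With a = P(A), b = P(B) and correlation ρ, P(A and B) = ab + ρ√[a(1−a)b(1−b)].

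For a = 0.5 and b = 0.6, ab = 0.30 and the root is √0.06 = 0.245.

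- ρ = 0: both 0.30; either 1.10 − 0.30 = 0.80; excess 50 points.
- ρ = 0.3: both 0.30 + 0.073 = 0.373; either 0.727; excess 35 points.
- ρ = 0.5: both 0.30 + 0.122 = 0.422; either 0.678; excess about 26 points.

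Other assumed pairs (either / both required):

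| a, b | ρ = 0 | ρ = 0.5 |
|---|---|---|
| 0.4, 0.5 | 70% / 20% | 58% / 32% |
| 0.6, 0.7 | 88% / 42% | 77% / 53% |
| 0.5, 0.8 | 90% / 40% | 80% / 50% |

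Over these four pairs and ρ from 0 to 0.5, the excess runs from about 24 to 50 points. If the dependence is left unrestricted, the first pair alone allows anything from 10 points (P(A and B) = 0.5) to 90 points (P(A and B) = 0.1).

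**Difference between arms (assumed, independent).** Suppose each compartment has progression probability p1 in control and p2 in the experimental arm. The arm difference is (p1 − p2)(p1 + p2) under *or* and (p1 − p2)(2 − p1 − p2) under *and*.

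- 40% to 30%: or 0.10 × 0.70 = 7 points; and 0.10 × 1.30 = 13 points.
- 70% to 60%: or 0.10 × 1.30 = 13 points; and 0.10 × 0.70 = 7 points.

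With unequal control rates moving from (0.4, 0.5) to (0.5, 0.6), both rules give 10 points: 0.80 − 0.70 and 0.30 − 0.20. The literal rule can therefore shrink, widen or leave unchanged the arm difference.

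**The case against.** The strongest defence is that *and/or* was meant to cover soft-tissue-only, bone-only and mixed disease in one phrase. Section 3.4.7.1 supplies a motive: "Measurable disease occurs infrequently in prostate cancer, whereas bone metastases develop in upwards to 90% of patients". That intention is plausible, but it is not written, and nothing in the protocol tells an analyst to apply it. The defence stands as an explanation of the wording; it does not supply a rule for patients with disease in both compartments.

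Three stronger readings are tempting, and the documents do not support them.

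- A reader might infer that the literal definition always compresses the treatment difference. It does so, with equal independent rates, only when p1 + p2 is below 1. Sections 1.1.2 and 3.4.2 put progression-free survival at about 3 months after two failed lines, so progression above 50% is plausible.
- A reader might infer that DCR contradicts rPFS wherever a controlled patient also has an rPFS event. Some overlap is normal: a best response of stable disease may precede later progression, and that patient belongs in both counts under any sensible definition. The fault is confined to patients whose best outcome in one compartment is progression.
- A reader might infer that Section 6.4.3 restricts DCR to patients with measurable soft tissue disease. It borrows methodologies, which may mean only the interval methods, and Section 6 attaches the restriction to ORR alone. What can be said is that the DCR denominator is not stated.

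The illustration also overstates what the whole trial would show: it concerns patients with disease in both compartments. A bone-only patient with confirmed bone progression has no soft tissue response and is uncontrolled under either rule.

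**Conclusion.** The definition is wrong as written, at low severity. It counts some patients with progression in one compartment as controlled. The direction is certain: each arm's rate is at least as high as one requiring control in every involved compartment, by the share of discordant patients. The size is not determinable from the documents. The 80% against 30%, and 68% against 42%, rest on assumed control rates of 0.5 and 0.6 with correlations of 0 and 0.5. *Too high* is relative to control in every involved compartment, and it applies to the rate in each arm, not necessarily to the treatment contrast.

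Section 6.4.2 confines formal testing to overall survival and the key secondary endpoints, so no primary or key secondary conclusion is affected. The study is closing for futility (Section 3.3), but DCR remains a listed analysis and Section 9.5 foresees publication of exploratory data.

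**What to change.** In Table 1 and the synopsis, define disease control as both of the following:

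- where soft tissue disease is present at baseline, a best response of confirmed CR, confirmed PR, stable disease or Non-CR/non-PD in soft tissue; and
- no confirmed progression on bone scan.

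Add that new lesions in a compartment uninvolved at baseline count as progression. Non-CR/non-PD has to be named because Appendix 3, Table 2, assigns that category, and advises against stable disease, for patients with non-target lesions only. Without it, non-progressing patients with non-measurable soft tissue disease would be classed as uncontrolled.

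In Section 6.4.3, state that:

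- the denominator is ITT patients with evaluable disease in either compartment, with only the ORR interval methods borrowed;
- bone status is judged at a named timepoint; and
- patients without a post-baseline assessment count as not controlled.

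The cost is a few sentences in three places, or in the SAP before analysis, with no new data collection. The downside is that the reported DCR will be lower.

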**Table 1 Objectives and Corresponding Endpoints (cont.)**

Safety Objective	Corresponding Endpoints

 
•To evaluate the safety and tolerability of atezolizumab and enzalutamide compared with enzalutamide alone
 
	
 
•Incidence, nature, frequency, and severity of adverse events, with severity determined through use of the National Cancer Institute Common Terminology Criteria for Adverse Events (NCI CTCAE v4.0)
 
•Clinically significant changes in vital signs, and clinical laboratory results during and following study treatment administration
 

Pharmacokinetic Objectives	Corresponding Endpoints

 
•To characterize the pharmacokinetics of atezolizumab when given in combination with enzalutamide
 
•To characterize the pharmacokinetics of enzalutamide and its active metabolite N-desmethyl enzalutamide when enzalutamide is administered alone or in combination with atezolizumab
 
	
 
•Serum concentration of atezolizumab at specified timepoints
 
•Plasma concentration of enzalutamide and N-desmethyl enzalutamide at specified timepoints in the safety run-in phase and in a PK cohort in the randomized phase (approximately 30 patients per treatment arm)
 

Exploratory Biomarker Objective	Corresponding Endpoints

 
•To identify biomarkers that are predictive of response to atezolizumab and/or enzalutamide (i.e., predictive biomarkers), are associated with progression to a more severe disease state (i.e., prognostic biomarkers), are associated with acquired resistance to atezolizumab and/or enzalutamide, are associated with susceptibility to developing adverse events, can provide evidence of atezolizumab and/or enzalutamide activity, or can increase the knowledge and understanding of disease biology on the basis of the following endpoint:
 
	
 
•Relationship between biomarkers in blood, urine, and tumor tissue (listed in Section 4.5.6) and efficacy, safety, PK, immunogenicity, or other biomarker endpoints
 

**Table 1 Objectives and Corresponding Endpoints (cont.)**

Immunogenicity Objective	Corresponding Endpoint
•To evaluate the immune response to atezolizumab	•Incidence of anti-therapeutic antibodies (ATAs) against atezolizumab
Exploratory Immunogenicity Objective	Corresponding Endpoint
•To evaluate potential effects of ATAs	•Relationship between ATA status and efficacy, safety, or PK endpoints

AQA= analgesic quantification algorithm; ATA= anti-therapeutic antibody; CR= complete response; CRPC= castration-resistant prostate cancer; DCR= disease control rate; DOR= duration of response; ECOG= Eastern Cooperative Oncology Group; NCI CTCAE= National Cancer Institute Common Terminology Criteria for Adverse Events; OS= overall survival; PCWG3= Prostate Cancer Working Group 3; PF= physical function; PFS= progression-free survival; PK= pharmacokinetic; PR= partial response; PSA= prostate-specific antigen; rPFS= radiographic progression-free survival; RECIST= Response Evaluation Criteria in Solid Tumors; SSE= symptomatic skeletal event.

### **3. STUDY DESIGN**

[figure not shown]
#### **3.1 DESCRIPTION OF THE STUDY**

This is a Phase III, multicenter, randomized, open-label study designed to evaluate the safety and efficacy of atezolizumab in combination with enzalutamide compared with enzalutamide alone in patients with mCRPC after failure of an androgen synthesis inhibitor (e.g., abiraterone) and failure of, ineligibility for, or refusal of a taxane regimen.

Specifically, the study will include the following patients:

- Patients who have progressed during treatment with an androgen synthesis inhibitor (e.g., abiraterone) for prostate cancer and have received a prior taxane regimen for metastatic hormone-sensitive and/or metastatic castration-resistant prostate cancer
- Patients who have progressed during treatment with an androgen synthesis inhibitor (e.g., abiraterone) for prostate cancer and who are not fit enough to receive a taxane regimen for mCRPC
- Patients who have progressed during treatment with an androgen synthesis inhibitor (e.g., abiraterone) for prostate cancer and who decline a taxane regimen for mCRPC after an informed discussion

**Figure 1 Study Schema**

CRPC = castration-resistant prostate cancer; iDMC = independent Data Monitoring Committee.

Notes: Enzalutamide: 160 mg orally per day. Atezolizumab: 1200 mg by IV infusion on Day 1 of each 21-day cycle. Treatment will continue until lack of clinical benefit, worsening of symptoms, decline in performance status, or tumor progression at a critical site that cannot be managed with protocol-accepted therapy. No crossover will be allowed from the control arm to the experimental arm.

Safety run-in phase: Ten patients will be followed for at least 1 cycle (21 days) after which the iDMC will make a recommendation regarding initiating enrollment in the randomized phase of the study. Patients in the safety run-in phase will continue to receive study treatment and be followed for safety and efficacy.

Approximately 180 sites globally will participate in the study and approximately 730 patients will be enrolled (first 10 patients in the safety run-in cohort followed by 720 patients in the global randomized phase).

The Sponsor recommends that investigators use their clinical judgment to determine if the patients who remain on the study appear to be benefitting from their therapy, and discuss the benefits and risks with patients of remaining on their current treatment. Patients who remain on treatment until the closure of the study will be able to continue to receive treatment as part of a post-trial access program. Patients may start transferring to the program after the required approvals are available (as applicable).

### **Safety Run-In Phase**

In the safety run-in phase of the study, 10 patients will be enrolled and will receive atezolizumab in combination with enzalutamide. After 10 patients have been enrolled, enrollment will be stopped temporarily and all patients will be monitored closely for adverse events until the last patient has completed the first cycle (21 days). Patients will continue to receive study treatment and be followed for safety and efficacy per the schedule of activities in [Appendix 1](#).

After 10 patients have received study treatment and completed at least one cycle of study treatment (21 days), an independent Data Monitoring Committee (iDMC) will review available data and make a recommendation regarding initiation of the randomized phase of the study. For further information on the iDMC, see [Section 3.2](#).

## Randomized Phase

Enrollment in the randomized phase of the study will be initiated after review of the safety run-in data by the iDMC and the Sponsor. Approximately 720 patients will be enrolled in the randomized phase of the study. Patients will be randomized to one of the following treatment arms in a 1:1 ratio (experimental to control arm):

- Arm A (experimental arm): atezolizumab in combination with enzalutamide
- Arm B (control arm): enzalutamide alone

Randomization will be conducted with the aid of an interactive voice/Web response system (IxRS).

The randomization will be stratified by the following stratification factors:

- Prior taxane-containing regimen for mCRPC, defined as at least two cycles of a taxane-containing regimen (yes vs. no)
- Presence of liver metastasis (yes vs. no)
- LDH  $\leq$  upper limit of normal (ULN) vs.  $>$  ULN
- Pain severity (BPI-Short Form [SF] Question 3 assessing pain at its worst over the past 24 hours [score  $<$  4 vs.  $\geq$  4]) ([Appendix 7](#))

A stratified permuted-block randomization will be implemented to balance treatment assignment within stratum levels.

Patient recruitment will be capped with respect to two of the stratification factors: the proportion of patients who have not received a prior taxane-containing regimen for mCRPC will be approximately 50% or less, and the proportion of patients with liver metastases at baseline will be approximately 10% or less. Presence of liver metastases will be determined based on CT or MRI scan. The purpose of the cap is to ensure the prevalence of these two prognostic factors in the study population will be similar to that reported in the targeted population.

Atezolizumab will be administered at a fixed dose of 1200 mg by IV infusion on Day 1 of each 21-day cycle until investigator-assessed confirmed radiographic disease progression per PCWG3 or unacceptable toxicity.

Enzalutamide will be administered orally at a dose of 160 mg (four 40-mg capsules) daily until investigator-assessed confirmed radiographic disease progression per PCWG3 or unacceptable toxicity.

Patients will be permitted to continue study treatment after PCWG3 criteria are met for confirmed radiographic disease progression if they meet all of the following criteria (treatment until they are no longer clinically benefiting per PCWG3 recommendation [Scher et al. 2016]).

- Evidence of clinical benefit as assessed by the investigator
- Absence of symptoms and signs indicating unequivocal progression of disease
- No decline in ECOG performance status that can be attributed to disease progression
- Absence of tumor progression at critical anatomical sites (e.g., leptomeningeal disease) that cannot be managed and stabilized by protocol-allowed medical interventions
- Written consent to acknowledge deferring other treatment options in favor of continuing study treatment at the time of initial disease progression

No crossover will be allowed from the control arm to the experimental arm.

Patients with rising PSA levels only (i.e., in the absence of confirmed radiographic or clinical progression) should continue to receive study treatment per PCWG3 criteria and recommendations (Scher et al. 2016). PSA rise without evidence of confirmed radiographic progression or a symptomatic skeletal-related event is strongly discouraged as a criterion to start a new systemic anti-neoplastic therapy during the first 12 weeks of therapy and is discouraged as a criterion to start a new systemic anti-neoplastic therapy throughout the study.

Focal palliative radiography (e.g., external-beam radiotherapy to address single sites of disease), initiation of bisphosphonates or denosumab, standard-of-care corticosteroid use of no greater than the equivalent of 10 mg of prednisone or prednisolone per day and pain management are allowed and should not result in discontinuation of study treatment. However, patients should be evaluated for clinically apparent SSE.

Initiation of radium-223 dichloride to manage symptomatic bone lesions is not permitted during study treatment.

Patients will undergo scheduled tumor assessments at baseline and every 9 weeks ( $\pm 3$  days) for the first 27 weeks and every 12 weeks ( $\pm 6$  days) thereafter until confirmed radiographic disease progression per PCWG3. In the absence of confirmed radiographic progression, tumor assessments should continue, regardless of whether patients start new anti-cancer therapy, until death, loss of follow-up, withdrawal of consent, or study termination by the Sponsor, whichever occurs first. For patients who continue to receive study treatment following confirmed disease progression, assessments will continue until loss of clinical benefit.

All primary imaging data used for tumor assessments may be collected by the Sponsor to enable the possibility of a centralized, independent review of response endpoints by an Independent Review Facility (IRF).

Safety assessments will include the incidence, nature, and severity of adverse events and laboratory abnormalities graded per the National Cancer Institute Common Terminology Criteria for Adverse Events, Version 4.0 (NCI CTCAE v4.0). Laboratory safety assessments will include the regular monitoring of hematology and blood chemistry.

Serum samples will be collected in patients in Arm A (atezolizumab and enzalutamide) to monitor atezolizumab pharmacokinetics and to detect the presence of antibodies to atezolizumab. Plasma samples to monitor enzalutamide and N-desmethyl enzalutamide pharmacokinetics will also be collected in the safety run-in phase and in a PK cohort in the randomized phase (approximately 30 patients per treatment arm). Patient samples, including archival tumor tissues, as well as urine, serum, plasma and whole blood, will be collected for future exploratory biomarker assessments for all patients in the randomized phase.

It is recommended that patients undergo tumor biopsy sample collection, if deemed clinically feasible by the investigator, at the time of first evidence of confirmed radiographic disease progression according to PCWG3 criteria (within 40 days after confirmed radiographic progression or prior to the start of new anti-cancer treatment, whichever is sooner). These samples will be analyzed to evaluate the utility of the biopsy in distinguishing pseudoprogression (caused by tumor-infiltrating ICs) from true progression. In addition, tumor tissue biomarkers related to resistance, disease progression, and clinical benefit of atezolizumab may be analyzed.

Patients who are withdrawn from study treatment will be evaluated within 30 days and approximately 120 days after last study treatment for a treatment discontinuation visit and safety visit, respectively. Thereafter, patients will enter a post-trial access program (as applicable).

An external iDMC will evaluate safety and efficacy data according to policies and procedures detailed in an iDMC Charter (see Section 3.2).

A schedule of activities is provided in [Appendix 1](#).

